Official Title: The HistoSonics System for treatment of primary and metastatic liver tumors using

histotripsy (#HOPE4LIVER US)

NCT Number: NCT04572633

Protocol Date: February 15, 2022 (CSP1427 Revision F)

Title	The HistoSonics System for treatment of primary and metastatic liver tumors using histotripsy (#HOPE4LIVER US)
Clinical Investigation Protocol Identification Code	#HOPE4LIVER US Sponsor Clinical Study Number: CSP1427 Revision F (15Feb2022) ClinicalTrials.gov Identifier: NCT04572633
Trial Purpose	The #HOPE4LIVER US clinical trial data will be utilized to gain approval in commercializing the HistoSonics System.
Trial Design	This trial is a single arm, non-randomized prospective trial. Following histotripsy treatment of liver tumor(s), subjects will undergo imaging ≤36 hours post-index procedure to determine technical success. Subjects will then be followed for 30 days. Additionally, subjects will be evaluated at 6 months and followed annually for up to five (5) years post-index procedure.
Trial Population	Subjects who are 18 years of age or older with a diagnosis of primary or metastatic (from other primary cancers) liver cancer.
Objective	The objective of this trial is to evaluate the efficacy and safety of the HistoSonics System for the treatment of primary or metastatic tumors located in the liver.
Device Name	HistoSonics System (System)
IDE Indications for Use	The HistoSonics System is intended for the destruction of liver tissue using histotripsy, a non-thermal, mechanical process using focused ultrasound.
Enrollment	Up to forty-five (45) subjects enrolled targeting forty (40) evaluable subjects at up to eight (8) US clinical sites
Duration of Trial	The duration of this trial is expected to be approximately six and a half (6.5) years.
Primary Endpoints	Co-primary endpoints:
	 Efficacy: Technical success as determined, at ≤36 hours post-index procedure, by evaluating the histotripsy treatment size and coverage. Technical success is defined as the treatment volume/treatment dimensions being greater than or equal to the targeted tumor with complete tumor coverage, via CT or MR imaging. [Core Lab Adjudicated] [≤36 hours post-index procedure]
	2. Safety: Index procedure related major complications, including device-related events, defined as Common Terminology Criteria for Adverse Events (CTCAE) grade 3 or higher toxicities, up to 30 days post index-procedure
	[Clinical Events Committee Adjudicated] [30-Day post-index procedure]
	Results must be positive for both co-primary endpoints for the trial to be considered successful.
Secondary Endpoints	Efficacy:
	Technique Efficacy: defined as the lack of a nodular or mass-like area of enhancement within or along the edge of the treatment volume assessed via MR or CT imaging at 30-days post index-procedure [Core Lab Adjudicated]
	Safety:
	All adverse events reported within 30 days of index-procedure [Clinical Events Committee Adjudicated]

Follow-Up Visits	All enrolled subjects will have a 14-day, 30-day, 6-month, and annual post-index procedure (1, 2, 3, 4, 5 year) follow up assessment/visit or until the trial is closed, whichever comes first.
General Inclusion	Subjects are eligible for the trial if all the following criteria are met:
	1. Subject is ≥18 years of age
	2. Subject has signed the Ethics Committee (EC) or Institutional Review Board (IRB) approved trial Informed Consent Form (ICF) prior to any trial related tests/procedures and is willing to comply with trial procedures and required follow-up assessments
	3. Subject is diagnosed with hepatocellular carcinoma (HCC) or liver metastases (mets) from other primary cancers
	 Subject that is an HCC patient must have a targetable lesion(s) which meets the United Network for Organ Sharing and Organ Procurement and Transplantation Network (UNOS-OPTN) class 5 diagnostic criteria for HCC
	 Subject that is diagnosed with liver metastases must have prior diagnosis of primary tumor or metastatic tumor to identify the primary cancer type. Subjects must have untreated new or growing liver tumor(s) radiologically consistent with metastases. Note: A biopsy is required to confirm metastatic disease and the pathological results must be obtained prior to the index procedure (does not need to be a targeted tumor(s))
	4. Subject is able to undergo general anesthesia
	5. Subject has a Child-Pugh Score of A or B (up to B8)
	6. Subject has an Eastern Cooperative Oncology Group Performance Status (ECOG PS) grade 0-2 at baseline screening
	7. Subject meets the following functional criteria, ≤7 days prior to the planned index-procedure date:
	 Liver function: Alanine transaminase (ALT) <2.5x upper limit of normal (ULN) and Aspartate transaminase (AST) <2.5x ULN and bilirubin <2.5 ULN, and
	Renal function: serum creatinine <2x ULN, and
	Hematologic function: neutrophil count >1.0 x 10^9/L and platelet >50 x 10^9/L
	8. Subject has an International Normalized Ratio (INR) score of <2.0, ≤7 days prior to the planned index procedure date
	 Subject has not responded to and/or has relapsed and/or is intolerant of other available therapies including locoregional therapies, chemotherapy, immunotherapy and targeted therapies.
Imaging Inclusion	10. The tumor(s) selected for histotripsy treatment must be ≤3 cm in longest diameter
	11. Subject has an adequate acoustic window to visualize targeted tumor(s) using ultrasound imaging
	12. Subject has a maximum of three (3) tumors to be treated with histotripsy during the index procedure, regardless of how many tumors the subject has.

	Note: If the subject is treated with surgical resection prior to the index procedure, the resection must be performed ≥2 weeks prior to the planned index-procedure date
General Exclusion	Subjects are not eligible for participation in the trial if any of the following criteria are met:
	Subject is pregnant or planning to become pregnant or nursing (lactating) during the trial period
	 Subject is enrolled in another investigational trial and/or is taking investigational medication and/or has been treated with an investigational device ≤30-days prior to planned index procedure date
	3. In the Investigator's opinion, the subject has co-morbid disease(s) or condition(s) that would cause undue risk and preclude safe use of the HistoSonics System
	4. Subject has a serum creatinine >2.0 mg/dL or estimated glomerular filtration rate (EGFR) <30, unless on dialysis
	 Subject has major surgical procedure or significant traumatic injury ≤2 weeks prior to the planned index procedure or not fully recovered (CTCAE grade 1 or better) from side effects/complications of such procedure or trauma
	6. Subject has not recovered to Common Terminology Criteria for Adverse Events (CTCAE) grade 1 or better from any adverse effects (except alopecia, fatigue, nausea, vomiting and peripheral neuropathy) related to previous anti-cancer therapy
	7. Subject has a history of, or suspected to have, bleeding disorders that are uncorrectable.
	8. Subject has a coagulopathy that is uncorrectable
	9. Subject has a planned cancer treatment (e.g. resection, chemotherapy, etc.) after the planned index-procedure date and prior to completion of the 30-day follow-up visit
	10. Subject has previous treatment with bevacizumab that has not been discontinued >40 days prior to the planned index-procedure date
	11. Subject has planned bevacizumab treatment prior to completion of the 30-day follow-up visit
	12. Subject has previous treatments with chemotherapy and/or radiotherapy that has not been discontinued ≥2 weeks prior to the planned index-procedure date and has not recovered (CTCAE grade 1 or better) from related toxicity (except alopecia and peripheral neuropathy)
	13. Subject has previous treatment with immunotherapies that has not been discontinued ≥4 weeks prior to the planned index-procedure date and has not recovered from related toxicity (CTCAE grade 1 or better)
	14. Subject has a life expectancy less than six (<6) months
	15. In the opinion of the Investigator, histotripsy is not a treatment option for the subject

	16. Subject has a concurrent condition that, in the investigator's opinion, could jeopardize the safety of the subject or compliance with the protocol
	17. Subjects' tumor(s) is not treatable by the System's working ranges (refer to User Manual)
	18. Subject has a known sensitivity to contrast media and cannot be adequately premedicated
	19. Subjects' targeted tumor(s) has/have had prior locoregional therapy (e.g. ablation, embolization, radiation)
	20. Subject is eligible for surgical resection
Imaging Exclusion	21. Targeted tumor(s) treatment volume overlaps a non-targeted tumor visible via imaging
	22. The targeted tumor(s) is not clearly visible with diagnostic ultrasound and computed tomography (CT) or magnetic resonance (MR) imaging
	23. The targeted tumor(s) is located in liver segment 1
	24. The Planned Treatment Volume intended to cover the targeted tumor includes or encompasses any portion of the main portal vein, common hepatic duct, common bile duct, gallbladder or stomach/bowel.
Statistical Methods	The primary efficacy and safety endpoints are based on a comparison to pre-specified performance goals established from relevant literature.
	Primary Efficacy
	A lesion success performance goal of 70% was established and the hypothesis was as follows:
	Null hypothesis: HistoSonics technical success rate ≤70%
	Alternative hypothesis: HistoSonics technical success rate >70%
	The proportion of observed Technical Success by lesion on those with evaluable imaging will be reported. As up to 3 treated lesions are allowed per subject, the 95% confidence interval for the observed Technical Success rate will be estimated by the bootstrap sampling with replacement method to account for potential within-subject lesion correlations. A subject will be the bootstrap sampling unit. A > 70% lower limit for the 95% confidence interval will indicate the HistoSonics Technical Success rate as statistically significantly higher than the performance goal of 70% at a 1-sided p < 0.025 level.
	Primary Safety
	A safety performance goal of 25% was established and the hypothesis was as follows:
	Null hypothesis: HistoSonics major complications patient incidence rate ≥25%
	Alternative hypothesis: HistoSonics major complications patient incidence rate <25%
	The patient incidence rate of index-procedure related major complications and its two-sided 95% Wilson Score CI will be calculated based on all subjects enrolled. The upper limit of the 95% CI must be <25% in order to regard the index procedure's safety as acceptable.

Secondary endpoints will be presented descriptively with no hypothesis test.

Determination of Sample Size

A literature review was conducted to identify rates of technical success in published studies on microwave and radiofrequency ablation of primary and metastatic liver tumors from 2010 to 2020. Eight studies reporting on 2,876 total tumors were assessed with a mean, weighted mean, and median rate of 81.5%, 86.6%, and 92.0%, respectively^{1–8}. Sample size was determined from primary efficacy of technical success assuming one treated lesion per subject for simplicity. Forty evaluable subjects were targeted for enrollment. Using a technical success acceptance level of 85% (34/40 lesions), which is consistent with the literature review results, the Wilson Score 95% confidence interval is 70.9% to 92.9%. Using the lower limit of the 95% confidence interval, a null hypothesis of ≤70% success rate can be rejected at a 1-sided p<0.025 significance level. By binomial probability calculation, the false positive (alpha) error for this design is 0.024. Assuming a true histotripsy technical success rate of 90%, the power for observing ≥34/40=85% in the trial is approximately 0.90. Due to the allowance of up to three (3) treated lesions per subject, the actual 95% confidence interval for the lesion based technical success rate would be estimated by the bootstrap sampling with replacement method and subject would be the sampling unit. The confidence interval would be narrower, and the power would be higher than the above estimates.

A similar review of major complications (CTCAE grade 3 or higher equivalent) when treating liver lesions with radiofrequency ablation identified 5 independent studies reporting on 1,935 patients and one review article encompassing 32 studies^{1–5,9}. Major complication rates ranged from 2.0% to 11.2%. For a new technology such as histotripsy, a conservative assumption for major complications was assumed to be close to the upper end of the literature results of 11.2%. Accordingly, with the sample size of 40 participants and a histotripsy major complication rate of 10% (4/40 participants), the Wilson Score 95% confidence interval is 4.0% to 23.1%. Assuming a true histotripsy event rate of 7%, the power of observing <4/40=10% in the trial is approximately 0.85.

A 5% - 10% attrition rate was anticipated; reasons for attrition included: both anticipated and unanticipated drop-out (e.g., subject withdrawal, loss-to-follow-up, and death) as well as the inability for the Core Laboratory to assess the primary efficacy endpoint due to missing or non-evaluable imaging. Therefore, up to forty-five (45) subjects were targeted for enrollment; subject replacement was not applicable in these cases.

Primary Analysis

The primary analyses of all primary and secondary endpoints will be performed after forty (40) evaluable subjects have been enrolled between the #HOPE4LIVER US (NCT04572633) and #HOPE4LIVER EU/UK (NCT04573881) trials and after those subjects have finished the 30-day assessment. This analysis will include at a minimum 10 subjects (25%) enrolled in the US. Data will be pooled between the two studies for the purposes of assessing the primary endpoints.

Bibliography

	2. Kim Y sun, Lim HK, Rhim H, et al. Ten-year outcomes of percutaneous radiofrequency ablation as first-line therapy of early hepatocellular carcinoma: analysis of prognostic factors. J Hepatol . 2013;58(1):89-97. doi:10.1016/j.jhep.2012.09.020

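### Exclusions 12 and 13 exclude for recent chemotherapy, radiotherapy or immunotherapy only if toxicity is also unrecovered, so the 2-week and 4-week periods never act on their own (minor wording fix)

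*Combined protocol and SAP*

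**What the plan says.** The General Exclusion list opens with the rule that "Subjects are not eligible for participation in the trial if any of the following criteria are met". Each criterion therefore has to be true as a whole before it excludes anyone.

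- Exclusion 12 concerns previous chemotherapy and/or radiotherapy that "has not been discontinued ≥2 weeks prior to the planned index-procedure date and has not recovered" to CTCAE grade 1 or better. Alopecia and peripheral neuropathy are exempt.
- Exclusion 13 concerns previous immunotherapy "that has not been discontinued ≥4 weeks prior to the planned index-procedure date and has not recovered from related toxicity". It exempts no toxicity.
- Exclusion 6 requires recovery to grade 1 or better from earlier anti-cancer therapy, with no time limit and a longer exemption list: "except alopecia, fatigue, nausea, vomiting and peripheral neuropathy".
- Exclusion 5, on major surgery or trauma, joins time and recovery the other way: "≤2 weeks prior to the planned index procedure or not fully recovered (CTCAE grade 1 or better").
- Exclusion 10 sets a period with no toxicity condition, for "previous treatment with bevacizumab that has not been discontinued >40 days prior to the planned index-procedure date". The note under Imaging Inclusion does the same for surgical resection, at 2 weeks.

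**The concern.** A washout period normally excludes on timing alone, because a subject may look well shortly after a dose and become unwell later. Here the named periods cannot do that. A subject with recent chemotherapy, radiotherapy or immunotherapy and no unrecovered toxicity can go to general anesthesia and histotripsy without meeting exclusion 12 or 13.

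Inclusion 9 calls for failure, relapse or intolerance after other available therapies, chemotherapy and immunotherapy among them. Earlier treatment is therefore plausible in this population, although that criterion does not say how recent it is. Sites may also differ: one may read the periods as stand-alone washouts, another may apply the literal text. What is at stake is protection of the individual subject and uniform eligibility. A lesser consequence is that toxicity from recent therapy may enter the 30-day record of all adverse events, a secondary endpoint reported descriptively.

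**Working it through.** **Reading the conjunction.** In both criteria the negative is repeated in each half. The form is (not stopped in time) AND (not recovered). It is not NOT (stopped in time AND recovered), which would exclude on either failure.

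**Looking for the period elsewhere in the criteria.**

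- Exclusion 2 covers investigational products only.
- Exclusion 6 has no time element.
- Exclusion 9 covers "planned cancer treatment (e.g. resection, chemotherapy, etc.) after the planned index-procedure date and prior to completion of the 30-day follow-up visit", which looks forward from the procedure.
- Exclusion 10 covers bevacizumab only.
- Exclusion 19 applies where the "targeted tumor(s) has/have had prior locoregional therapy (e.g. ablation, embolization, radiation"), so it is limited to locoregional therapy of the target.
- Exclusions 3, 15 and 16 rest on investigator judgement and name no period.
- Inclusions 7 and 8 set laboratory and INR limits on results from the 7 days before the procedure. If the last dose was more than 7 days before the procedure, those results must follow it. They can pre-date it only when the dose fell within the last 7 days: 7/14 = one half of the 2-week period and 7/28 = one quarter of the 4-week period.

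None of these sets a general 2-week or 4-week washout.

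**Enumerating the cases.** Take six kinds of unrecovered toxicity, each present or absent: alopecia, neuropathy, fatigue, nausea, vomiting and any other. That gives 2^6 = 64 combinations, for therapy inside and outside the period, or 128 cells per therapy.

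- Exclusion 6 is true when *other* is present: 32 of 64, inside or outside.
- Literal exclusion 12 is true inside the period when fatigue, nausea, vomiting or other is present. It is false for the 2^2 = 4 combinations of alopecia and neuropathy alone, including neither: 64 − 4 = 60.
- Literal exclusion 13 is true inside the period when any toxicity is present: 64 − 1 = 63.

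| Rule, each with exclusion 6 | Excluded inside | Excluded outside | Eligible inside |
|---|---|---|---|
| Exclusion 6 alone | 32 | 32 | 32 |
| Exclusion 12 as written | 60 | 32 | 4 |
| Exclusion 13 as written | 63 | 32 | 1 |
| Stand-alone period (12 or 13) | 64 | 32 | 0 |
| 12 with *or*, present exemptions | 64 | 60 | 0 |
| 13 with *or*, present exemptions | 64 | 63 | 0 |

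A stand-alone period newly excludes 64 − 60 = 4 cells (exclusion 12) and 64 − 63 = 1 cell (exclusion 13), all inside the period, and makes no excluded cell eligible. A bare swap to *or* also excludes 60 − 32 = 28 and 63 − 32 = 31 cells outside the period. Those are subjects whose only unrecovered effects are ones that exclusion 6 deliberately exempts.

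**Reach into the safety co-primary.** The documents give no eligibility figure to reproduce, but they do give a Wilson interval for safety. The upper limit is [p + z²/2n + z√(p(1−p)/n + z²/4n²)] / (1 + z²/n), with z = 1.96. For 4/40 this is (0.1000 + 0.0480 + 0.1046)/1.0960 = 23.1%, matching the Determination of Sample Size section. For 5/40 it is (0.1250 + 0.0480 + 0.1132)/1.0960 = 26.1%. Safety is analysed on all enrolled subjects, and enrollment may reach 45: there 5/45 gives 23.5% and 6/45 gives 26.2%. Against the 25% goal, one extra event changes the verdict only if it is the fifth event at n = 40 or the sixth at n = 45.

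**The case against.** The strongest reply is that the text is coherent as it stands. Exclusion 6 demands recovery at any time, with five exempt effects. Inside the period, exclusion 12 cuts the exemptions to two and exclusion 13 to none, which can be read as a stricter recovery test for recent therapy. The comparators fit that reading too: the authors wrote *or* in exclusion 5 and a stand-alone period in exclusion 10, so they knew how to do both. This stands. A reader might infer a proven drafting error, or that the two criteria do nothing beyond exclusion 6. The documents support neither. Intent is not stated, and inside the period exclusion 12 adds fatigue, nausea and vomiting while exclusion 13 adds all five exempt effects.

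A second reply is that other safeguards apply. A subject treated recently must still pass the anesthesia, Child-Pugh, ECOG, laboratory and INR criteria, exclusion 6 and investigator judgement. For doses more than 7 days before the procedure, the laboratory and INR results do reflect the state after treatment. It would be wrong to dismiss them as possibly pre-dating the dose throughout the period. They are partial protection all the same: they show the subject's state when the sample was taken, and they do not impose the named period.

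A third reply is that nothing in the documents shows that recent therapy without unrecovered toxicity raises the risk of anesthesia or histotripsy. That is correct. The argument for change is precaution and clarity, not demonstrated harm.

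**Conclusion.** The point holds as a matter of wording and is minor. Read literally, the 2-week and 4-week periods never exclude anyone by themselves, and no other criterion supplies a general washout for these therapies. The gap is 4 of 64 logical toxicity states inside the period for exclusion 12 and 1 of 64 for exclusion 13. These counts carry no weights and say nothing about how many subjects are affected. The conclusion assumes that sites apply the text literally; some may already treat the periods as stand-alone.

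A reader might go further and infer that the safety co-primary is compromised. The documents do not support that. The endpoint counts procedure-related events adjudicated by the Clinical Events Committee, so a toxicity of earlier therapy would matter only if misattributed to the procedure, and it would alter the verdict only at the single event count shown above. That error would count against the device; the reverse error is conceivable, but nothing in the documents allows it to be sized. No effect on technical success is claimed, and no sample size, alpha, power or primary-endpoint figure changes.

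**What to change.** Make each period a stand-alone exclusion, as exclusion 10 already does, and leave recovery to exclusion 6:

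- Exclusion 12: chemotherapy and/or radiotherapy not discontinued ≥2 weeks before the planned index procedure.
- Exclusion 13: immunotherapy not discontinued ≥4 weeks before the planned index procedure.

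Changing *and* to *or* is equivalent only if both criteria also take exclusion 6's exemption list. Do not swap in *or* with the present lists. If *and* was deliberate, say so and state why recent therapy without toxicity is acceptable.

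The cost is a wording amendment to two criteria and a notice to sites, with no change to sample size or analysis, and no currently excluded subject becomes eligible. Any subjects affected would wait up to 2 weeks (chemotherapy or radiotherapy) or 4 weeks (immunotherapy). The wait lengthens time off treatment, since exclusion 9 already bars planned cancer treatment until the 30-day visit is complete, and it could cost eligibility if a target tumor grows beyond 3 cm.

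### The bootstrap interval for Technical Success shows no uncertainty when no lesion fails and too little when one fails; the decision against 70% is unaffected (minor)

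*Combined protocol and SAP*

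**What the plan says.** The Primary Efficacy part of Statistical Methods defines the estimate by lesion: "The proportion of observed Technical Success by lesion on those with evaluable imaging will be reported". Because a subject may have up to three treated lesions, it then states that "the 95% confidence interval for the observed Technical Success rate will be estimated by the bootstrap sampling with replacement method" and adds "A subject will be the bootstrap sampling unit". The null is "Null hypothesis: HistoSonics technical success rate ≤70" percent. It is rejected when the lower limit exceeds 70%, which the plan describes as significance "at a 1-sided p < 0.025 level". The bootstrap variant and the number of resamples are not given, and nothing is said about a result with no failures.

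Determination of Sample Size works with a different interval. It takes one lesion per subject, and for 34/40 "the Wilson Score 95% confidence interval is 70.9% to 92.9" percent. The same section then confirms that the actual analysis interval will be the bootstrap. The safety co-primary, under Primary Safety, uses the Wilson Score interval in the analysis itself.

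**The concern.** A bootstrap can only reproduce variation that is present in the sample. If every evaluable lesion is a success, every resample of subjects is also 100% successful. More resamples, a fixed seed or a named variant do not change that. The stated method would then claim certainty, or return nothing, for one of the two co-primary endpoints. With a single failure it returns an interval, but one that is short on the low side.

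The Trial Purpose section says that the data are meant to support commercialization, so the efficacy rate and its 95% interval are a main reported result. If the specified interval is unusable, a replacement has to be chosen after the data are seen, which prespecification is meant to prevent.

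**Working it through.** **Inputs.** From the documents: 40 evaluable subjects ("Forty evaluable subjects were targeted for enrollment"); goal 70%; planning rate ("Assuming a true histotripsy technical success rate of 90" percent); literature rates of 81.5% (mean), 86.6% (weighted mean) and 92.0% (median); up to three lesions per subject. Assumed here: a true rate of 95%, and a mix of 26, 8 and 6 subjects with 1, 2 and 3 lesions (26 + 16 + 18 = 60 lesions). The documents give neither.

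**1. The plan's own figures.** The Wilson limits are [p + z²/(2n) ± z√(p(1−p)/n + z²/(4n²))] / (1 + z²/n), with z = 1.96. For 34/40 this gives 70.9% to 92.9%. The exact binomial probability of 34 or more out of 40 is 0.0238 at 70% and 0.9005 at 90%. These agree with the stated interval, alpha of 0.024 and power of about 0.90.

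**2. No failures.** Each resample rate is successes divided by lesions, which is 1 whatever subjects are drawn. A simulated 40 subjects with 63 lesions, all successes, gave a resample standard deviation of 0 and an interval of 100% to 100%. For comparison:
- Wilson at p = 1 reduces to a lower limit of n/(n + z²) = 40/(40 + 3.84) = 91.2%.
- The exact lower limit is 0.025^(1/40) = 91.2%.
- With 45/45, both give 92.1%.

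**3. One failure (39/40, one lesion each).** The number of successes in a resample is binomial(40, 0.975). P(≤36) = 1.7% and P(≤37) = 7.8%, so the 2.5th percentile is 37/40 = 92.5% and the percentile interval is 92.5% to 100%. Wilson gives 87.1% to 99.6%.

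**4. How likely is zero failures, with one lesion per subject?** P = p^40.

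| True rate | Source | P(no failure in 40) |
|---|---|---|
| 81.5% | literature mean | 0.03% |
| 86.6% | literature weighted mean | 0.3% |
| 90% | plan's assumption | 1.5% |
| 92.0% | literature median | 3.6% |
| 95% | assumed here | 12.9% |

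Setting p^40 to 5% gives p = 92.8%; setting it to 10% gives p = 94.4%. At a true 95%, the coverage of the nominal 95% interval cannot exceed 100% − 12.9% = 87.1%.

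**5. The same with several lesions per subject.** For within-subject correlation ρ > 0, use a beta-binomial with a = p(1−ρ)/ρ and b = (1−p)(1−ρ)/ρ. The chance that all m lesions of a subject succeed is q_m = ∏(a+j)/(a+b+j) for j = 0 to m−1; at ρ = 0 it is p^m. For the 60-lesion mix, P(no failure) = q₁^26 × q₂^8 × q₃^6.

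| True rate | ρ = 0 | ρ = 0.3 | ρ = 0.6 |
|---|---|---|---|
| 90% | 0.2% | 0.4% | 0.7% |
| 92% | 0.7% | 1.2% | 2.0% |
| 95% (assumed) | 4.6% | 6.6% | 9.0% |

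**6. How likely is exactly one failure, with one lesion per subject?** P = 40 × p^39 × (1−p): 6.6% at 90% and 12.4% at 92%. The result in step 3 is therefore more likely at the plan's rates than the full collapse.

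**The case against.** The strongest reply is that the outcome is improbable and harmless. On the documents' own rates, zero failures has a probability between 0.03% and 3.6% with one lesion per subject, and of 2.0% or less at 90% to 92% in the 60-lesion mix. A reader might infer that the collapse is a realistic result for a device that works well. The documents do not support that, because it needs a true rate of about 95% or more with close to one lesion per subject. A median of 92.0% over eight studies shows that high rates occur in the literature, but the individual rates are not given. This part of the reply stands.

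A reader might also infer that the trial could be declared successful wrongly. It could not on this ground: with zero or one failure, every limit calculated here is far above 70%. That stands too. It is also true that a published count of 40/40 lets anyone compute a proper limit.

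Nor can one say that the plan will certainly print 100% to 100%. No variant is named, and for BCa or studentized forms the result is undefined. Either way, the specified method gives no usable interval.

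Finally, a switch of method at zero failures alone produces an anomaly: 40/40 would carry a lower limit of 91.2%, below the percentile bootstrap's 92.5% for 39/40. This is a sound objection to the narrowest remedy, and it shows that the remedy should also cover results near 100%.

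The reply does not remove the defect itself. The stated rule, followed as written, gives a wrong error bar or none for a co-primary endpoint.

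**Conclusion.** The point holds as a minor defect in the reported interval. With no failures among 40 subjects, the specified method gives 100% to 100% or nothing, where the data support a lower limit of about 91.2%. With 39/40, the percentile form puts the lower limit at 92.5% against 87.1% for Wilson, a difference of 5.4 percentage points. The collapse itself follows from the method under any lesion mix or correlation. The 91.2%, and both limits for 39/40, rest on 40 independent subjects with one lesion each.

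The issue described here leaves the test against 70%, the sample size and the stated power as they are. The zero-failure case is uncommon at the plan's rates (1.5% at 90% and 3.6% at 92.0% with one lesion per subject, less with more lesions). The 12.9% at a true 95% is conditional on a rate assumed from outside the documents.

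**What to change.** In the Primary Efficacy section, report the 95% interval for Technical Success as a Wilson Score interval adjusted for clustering by subject. The effective sample size is the number of evaluable lesions divided by the estimated design effect. When no lesion fails, the design effect cannot be estimated, so use the number of evaluable subjects as the denominator (40/40: 91.2% to 100%). That choice corresponds to complete within-subject correlation and is conservative otherwise. Name the design-effect estimator in advance, since it will be unstable with very few failures, and state that this interval is the one compared with 70%. Keep the subject-level bootstrap as a supporting analysis, with its variant and number of resamples given.

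At a minimum, add the zero-failure fallback alone, and note that it then gives a lower limit below the bootstrap limit for one failure.

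The cost is a sentence or two in the plan and a slightly less favourable reported lower limit. No change to the sample size is needed. With one lesion per subject, the Wilson interval is the one already used for sizing, and 34/40 remains the smallest passing result (33/40 gives 68.1%).
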